4.4.2.2. Other Safety Endpoints

The safety measures based on CGM data will be analyzed as described in Section 4.4.2.1. For other safety measures, the details are provided in Section 4.6.

4.4.2.3. Patient Reported Outcome

The analyses for patient-reported outcomes will be based on the EAS2 data.

4.4.2.3.1. *Treatment-Related Impact Measure – Diabetes (TRIM-D)*

The TRIM-D is a self-administered instrument, which assesses the impact of diabetes treatment on participants' functioning and well-being across available diabetes treatments (Brod et al. 2009). The TRIM-D consists of 28 items each assessed on a 5-point scale, where higher scores indicate a better health state, with a recall period of "over the past 2 weeks". In addition to an overall score, the TRIM-D items assess 5 domains of impact:

- Treatment Burden (6 items: Question 1a, Question 2a to 2e),
- Daily Life (5 items: Question 3a to 3b, Question 5a to 5c),
- Diabetes Management (5 items: Question 4a to 4e),
- Compliance (4 items: Question 6a, b, c, e), and
- Psychological Health (8 items: Question 6d, Question 7a to 7g)

Items within each domain are summed to obtain a raw domain score, which is then transformed to a scale of 0 to 100 to obtain a transformed domain score. The transformed domain score can be calculated by

$$\frac{(\text{sum of raw score} - \text{sum of lowest possible raw score})}{(\text{sum of highest possible raw score} - \text{sum of lowest possible raw score})} \times 100$$

For an example, Diabetes Management = $([\text{sum of raw score} - 5]/[25-5]) \times 100$. If answer for the 5 questions in Diabetes Management (Question 4a to 4e) are all 1, then the sum of raw score is 5 and the transformed domain score is 0. All items can also be summed and transformed to obtain a transformed total score in a similar way.

Summary statistics for the transformed scores of each domain will be provided by study treatment. The scores at scheduled visits and the change from baseline will be analyzed by the MMRM model similar to the other efficacy endpoints (see Section 4.4.2.1). The last non-missing postbaseline observations will be analyzed by an ANCOVA model using the independent variables of treatment, strata (country, GLP-1 RA treatment at randomization, SU use at randomization, and baseline HbA1c stratum), and baseline value of the dependent variable as independent variables.

4.4.2.3.2. *Short-Form-36 Health Survey Version 2, Acute Form*

Per copyright owner, the QualityMetric Health Outcomes™ Scoring (PRO_CoRe V2.0) Software will be used to derive the following domains:

- Physical Functioning domain,
- Role-Physical domain,
- Bodily Pain domain,
- General Health domain,
- Vitality domain,
- Social Functioning domain,
- Role-Emotional domain, and
- Mental Health domain.

and component summary scores:

- Mental Component Score, and
- Physical Component Score.

Each domain is scored individually, and information from these 8 domains is further aggregated into 2 health component summary scores, the Physical Component Summary and Mental Component Summary. Scoring of each domain and both summary scores are norm based and presented in the form of T-scores, with a mean of 50 and standard deviation of 10. Higher scores indicate better levels of function and/or better health (Maruish 2011).

Summary statistics for the component summary scores and scores in each domain will be provided by study treatment. The scores at scheduled visits and the change from baseline will be analyzed by the MMRM model similar to the other efficacy endpoints (see Section 4.4.2.1) for the scheduled postbaseline visits and by the ANCOVA model similar to the TRIM-D for the last non-missing postbaseline observations.

4.4.2.3.3. *EQ-5D-5L*

The EQ-5D-5L (EuroQol Research Foundation 2019) is a standardized 5-item self-administered instrument for use as a measure of health outcome. It provides a simple descriptive profile and a single index value for health status that can be used in the clinical and economic evaluation of health care as well as population health surveys. The EQ-5D-5L assesses 5 dimensions of health:

- mobility,
- selfcare,
- usual activities,
- pain/discomfort, and
- anxiety/depression.

The 5L version, scores each dimension at 5 levels:

- no problems,
- slight problems,
- moderate problems,
- severe problems, and
- unable to perform/extreme problems.

In addition to the health profile, a single health state index value can be derived based on a formula that attaches weights to each of the levels in each dimension. This index value ranges between less than 0 (where 0 is a health state equivalent to death; negative values are valued as worse than dead) to 1 (perfect health).

The second part of the questionnaire consists of EQ Visual Analog Scale (VAS) which records the respondent's self-rated health status. The participant rates his/her perceived health from 0 (the worst imaginable health) to 100 (the best imaginable health). In conjunction with the health state data, it provides a composite picture of the respondent's health status.

The frequency and proportion of each level for a given item will be summarized by study treatment for each scheduled visit. The EQ-5D-5L index, EQ VAS score and their change from baseline will be analyzed by the MMRM model similar to the other efficacy endpoints (see Section 4.4.2.1) for the scheduled postbaseline visits and by the ANCOVA model similar to the TRIM-D for the last non-missing postbaseline observations.

4.4.2.3.4. Simplicity Questionnaire (SIM-Q) Single Medication status version

The Simplicity of Diabetes Treatment Questionnaire (SIM-Q) single medication status version is a brief 10-item measure developed to assess the simplicity and complexity of treatment for T2D. This measure asks participants to think about a specific medication (prior basal insulin or current study treatment) when completing each item on a 5-point scale ranging from "Very complex" to "Very simple." In Study BDCX, only the last 2 questions of the SIM-Q will be completed – "How simple or complex is your medication treatment for diabetes?" and "Overall, how simple or complex is it to manage your diabetes, including medication, checking your blood glucose levels, diet, and any other aspects of diabetes treatment?"

The frequency and proportion of the response for each question will be summarized for each scheduled visit. Treatment comparison will be conducted by Wilcoxon rank sum test.

4.4.2.3.5. Basal Insulin Experience: Likelihood of incorporating into routine

This is a Lilly-developed, participant-completed question to understand the participant's likelihood of incorporating their study insulin into their diabetes management routine. The question is rated on a 5-point scale with responses ranging from "very unlikely" to "very likely."

The frequency and proportion of the responses will be summarized by study treatment and using Wilcoxon rank sum test for treatment comparison.

4.5. Tertiary Endpoints Analysis

4.5.1. Tertiary Subgroup Analyses

Subgroup analyses for GLP-1 RA use at randomization will be conducted by the methods described in Section 4.7.2.1.

4.5.2. Tertiary Efficacy Endpoints

For continuous endpoints, similarly to what described in Section 4.4.2.1 for the supportive secondary efficacy endpoints, either ANCOVA model using data from EAS1 or MMRM model using data from EAS2 will be performed.

For the binary outcome endpoints of percentage of participants at Week 52 achieving HbA1c <7%, HbA1c <7% without nocturnal level 2 or 3 hypoglycemia, HbA1c \leq 6.5% without level 2 or 3 hypoglycemia, and HbA1c <7% without level 2 or 3 hypoglycemia, EAS1 will be used for the analysis and the details are provided in the following table:

Analysis population	All participants in EAS1 with non-missing baseline measure
Analysis data	All non-missing observations at Week 52 (Visit 31) during treatment period regardless of the use of study intervention or rescue therapy
Endpoint	
 • Binary outcome of HbA1c <7% with 1 indicating achieving HbA1c target • The composite of: 
 ◦ binary outcome of HbA1c <7% at Week 52 with 1 indicating achieving HbA1c target; and ◦ binary outcome of no nocturnal hypoglycemia (<54 mg/dL or severe) during 52-week treatment period with 1 indicating no occurrence of nocturnal hypoglycemia. • The composite of: 
 ◦ binary outcome of HbA1c \leq6.5% at Week 52 with 1 indicating achieving HbA1c target; and ◦ binary outcome of no hypoglycemia (<54 mg/dL or severe) during 52-week treatment period with 1 indicating no occurrence of hypoglycemia. • The composite of: 
 ◦ binary outcome of HbA1c <7% at Week 52 with 1 indicating achieving HbA1c target; and ◦ binary outcome of no hypoglycemia (<54 mg/dL or severe) during 52-week treatment period with 1 indicating no occurrence of hypoglycemia.
Missing data handling	
 • For HbA1c, missing values at Week 52 (Visit 31) will be imputed using the same method for the primary endpoint. The binary outcomes of HbA1c <7% or \leq6.5% will be based on the imputed data. • For nocturnal hypoglycemia or hypoglycemia that are included in the composite endpoints, a participant who discontinued the treatment period before Week 52 (Visit 31) is considered as a non-responder (i.e. experienced the event) and the binary outcome value will be imputed as 0.

Analysis model	Each endpoint will be analyzed using a logistic regression model including treatment, strata (country, GLP-1 RA treatment at randomization and SU use at randomization), and baseline HbA1c value. The odds ratio between LY3209590 and insulin degludec will be used for treatment comparison. Multiple imputation will be performed, and the statistical inference will be based on the multiple imputation framework by Rubin (1987)
----------------	---

Abbreviations: EAS1 = Efficacy Analysis Set 1; GLP-1 RA = glucagon-like peptide-1 receptor agonist;

HbA1c = glycated hemoglobin; SU = sulfonylurea.

4.5.3. **Tertiary Safety Endpoints**

For tertiary safety measures, the details are provided in Section 4.6 and the following subsections.

4.6. **Safety Analyses**

Safety measures include treatment exposure, adverse events (AE), vital signs, weight, hypoglycemia, laboratory measures and immunogenicity. All safety analyses will be based on the SS. Unless otherwise specified, safety analysis period will include both treatment period and follow-up period.

Percentages will be calculated using the safety population as the denominator. For events that are gender-specific, the denominator and computation of the percentage will include only participants from the given sex. Unless otherwise noted, Fisher's exact test will be used for treatment comparison, risk difference and 95% confidence intervals will be provided.

For continuous safety variables (for example, laboratory measures, vital signs, and weight), descriptive statistics for the observed values and change from baseline at scheduled visits during the treatment and follow-up period will be provided. For selected laboratory measures (i.e. liver enzyme tests, lipid measures), observed values, change from baseline and percentage change from baseline will be analyzed for the log-transformed values by the MMRM model using treatment, visit, and treatment by visit as fixed effect, baseline of the dependent variable as a covariate, and compound symmetry as the variance-covariance structure.

The incidence and event rate of participant-reported and CGM-based hypoglycemia will be summarized by treatment and analysis period for different types of hypoglycemia. Analysis details are provided in Section 4.6.3.1.

4.6.1. **Extent of Exposure**

Duration of exposure to study treatment will be summarized. No p-values will be reported in these tables as they are intended to describe the study populations, rather than test hypotheses about them. Total patient-years of exposure will be reported. The number and proportion of participants falling into the following different exposure categories will also be summarized by study treatment:

- $>0, \geq 30$ days, ≥ 90 days, ≥ 180 days, ≥ 365 days; and
- >0 and <30 days, ≥ 30 and <90 days, ≥ 90 and <180 days, ≥ 180 and <365 days, ≥ 365 days.

Exposure on study treatment will be calculated as:

- LY3209590: date of the last treatment administration – date of first treatment administration + 7 days; and

- Insulin degludec: date of the last treatment administration – date of first treatment administration + 1 day.

Total patient-years of exposure will be calculated by the sum of duration of exposure in days divided by 365.25. The following summary statistics will be provided: n, mean, standard deviation, median, minimum, maximum, interquartile range, and total exposure (that is, total patient-years).

All participants who complete the study treatment period are required to complete a safety follow-up period and participants who discontinue the study treatment prematurely are encouraged to remain in the study for safety monitoring. The duration on study from the first dose of study treatment to the final study disposition date will also be summarized by treatment.

A listing of exposure to study treatment will be provided.

4.6.2. Adverse Events

Events that are newly reported after the first dose of investigational product (IP) or reported to worsen in severity from baseline will be considered treatment emergent adverse events (TEAEs). The Medical Dictionary for Regulatory Activities (MedDRA) lowest level term (LLT) will be used in the treatment-emergent assessment. The maximum severity for each LLT during the baseline period (see the table in Section 4.1) will be used as baseline severity.

The table below describes the analysis related to AEs.

Analysis	Details
Overview of AEs	
Number and percentage of participants who experienced:
 
 • SAE, • Death, • Discontinuation from study treatment due to an AE, • Discontinuation from study due to an AE, • TEAE, and • TEAE related to study treatment.
Summary by PT within SOC	
Number and percentage of participants with AEs using MedDRA PT nested within SOC:
 
 • TEAE, • Maximum Severity TEAEs, • SAE, and • AE leading to permanent discontinuation of study treatment. 
Events will be ordered by decreasing risk difference within SOC. SOCs will be listed by decreasing risk difference.
 
For each participant and TEAE, the maximum severity for the MedDRA PT is the maximum postbaseline severity observed from all associated LLTs mapping to the MedDRA PT. The maximum severity will be determined based on the non-missing severities.

Analysis	Details
Summary by PT (within SMQ when applicable)	
Number and percentage of participants with TEAEs using MedDRA PT (irrespective of SOC):
 
 • TEAEs occurring in $\geq 1\%$ before rounding in LY3209590 group, and • TEAE of safety topic of interest by PT (within SMQ when applicable). 
Events will be ordered by decreasing risk difference.

Listing	
Separate listings for the following AEs or events will be provided:
 
 • SAE including death; • AEs leading to study treatment discontinuation; • Severe hypoglycemia; • Events sent to the external adjudicator for MACE adjudication • Participants who receive rescue therapy due to severe/persistent hyperglycemia; • Persistent-recurrent hypoglycemia reported by investigators; • Persistent-recurrent hypoglycemia identified by programming; and • Medication errors of interest.

Abbreviation: AE = adverse event; LLT = lowest level term; MACE = major adverse cardiovascular event; MedDRA = Medical Dictionary for Regulatory Activities; SAE = serious adverse event; SOC = System Organ Class; PT = preferred term; TEAE = treatment emergent adverse event

4.6.2.1. Safety Topics of Interest

4.6.2.1.1. *Severe Hypoglycemia*

Severe hypoglycemia is a severe event characterized by altered mental and/or physical status requiring assistance for treatment of hypoglycemia. The determination of a hypoglycemic event as an episode of severe hypoglycemia is made by the investigator based on the medical need of the participant to have required assistance and is not predicated on the report of a participant simply having received assistance. If a hypoglycemic event meets the criteria of severe hypoglycemia, the investigator must record the event as serious on the AE case report form (CRF).

A summary of severe hypoglycemia by decreasing risk difference will be provided. The incidence and event rate during the treatment period will be analyzed using the method described in Section 4.6.3.1. A listing of severe hypoglycemia events will also be provided.

4.6.2.1.2. *Persistent-Recurrence Hypoglycemia*

The potential risk of persistent-recurrent hypoglycemia (P-R hypoglycemia) will be assessed from the first dose date up to the end of the study. P-R hypoglycemia events will be identified using:

1. investigator assessment and clinical judgment to determine if repeated hypoglycemia may have contributed to a hypoglycemic event that degenerated with poor outcomes, and
2. a prespecified criteria to derive events from e-diary database by programming (see definition in [Appendix 10](#) [Section 6.10]).

Identification of P-R hypoglycemia based on investigator reporting is precipitated by a hypoglycemic event a participant or their caregiver informed as having resulted in a poor outcome. This information will trigger an e-mail alert notifying the investigator to contact the study participant, obtain more information about the specific hypoglycemic event, and provide the participant clinical guidance, if appropriate. Hypoglycemic events that trigger alerts to investigators are those participants or caregivers report in the e-Diary have required treatment with glucagon or IV glucose, resulted in coma, motor vehicle accident or other trauma, hospitalization, or emergency medical care.

Upon receiving the e-mail notification, investigator will access the e-diary database and answer the following question: *"In your clinical judgement, is this hypoglycemia event associated with repeated hypoglycemia events?"*. Investigator should select "Yes" or "No" as an answer.

During protocol training, investigators are trained to consult the e-diary database and review participant's BG values and hypoglycemia reports to determine the best answer. If investigator judges the hypoglycemic event that triggered an alert is related to repeated episodes of hypoglycemia, the participant will be identified as having presented a P-R hypoglycemic event reported by the investigator.

P-R hypoglycemia events and participants who present P-R hypoglycemia will be identified by 1 or both approaches explained above. Summary statistics and a listing of the events identified by both methods will be provided.

4.6.2.1.3. Systemic Hypersensitivity Reactions

Hypersensitivity reactions are exaggerated or inappropriate immunologic responses occurring in response to an antigen or allergen. These can be systemic or localized. At all visits, participants will be evaluated by the investigator for signs and symptoms suggestive of hypersensitivity. Investigators will complete an CRF designed to record additional information about AEs suggestive of a hypersensitivity reaction. The TEAEs of hypersensitivity reactions were identified using:

- Anaphylactic reaction SMQ (20000021; narrow terms),
- Hypersensitivity SMQ (20000214; narrow terms), and
- Angioedema SMQ (20000024; narrow terms).

The number and percentage of participants who reported a TEAE for the following will be analyzed:

- Any narrow term from any 1 of the 3 SMQs indicated above (that is, combined search across narrow portions of all 3 SMQs), and
- Any narrow term within each SMQ, separately (that is, narrow SMQ search).

Individual PTs that satisfied the query will appear in the summary in decreasing order of risk difference between the LY3209590 and insulin degludec group.

The analyses above are the starting point for medical interpretation of any apparent differences between treatment groups. For notable events, case review will be applied to make the final determination of whether an event is most accurately described as a potential hypersensitivity reaction to study treatment, or another event that is not clearly associated with study treatment administration. This judgment will be on the basis of totality of information available, including the content of a follow-up CRF collected for potential hypersensitivity events.

4.6.2.1.4. *Injection Site Reactions*

Injection site reactions (ISR) are AEs localized to the immediate site of the administration of a medication. The evaluation of ISRs will be through the unsolicited reporting of ISR TEAEs and through the use of an Injection Site Reaction Follow-up Form completed by the investigator for each incidence of ISR. A summary of the number of participants with reported events meeting any of the following categories will be provided:

- MedDRA HLT of Injection site reactions;
- MedDRA HLT of Administration site reactions NEC;
- Lipodystrophies and localized amyloidosis, as represented by PTs of:
 - Lipoatrophy,
 - Lipodystrophy acquired,
 - Partial lipodystrophy,
 - Lipohypertrophy,
 - Sclerema, and
 - Cutaneous amyloidosis.

The summary will present:

- The number of participants reported at least one AE meeting any of the above categories,
- The number of participants reported any AE in each category, and
- The number of participants reported any AE for each PT within a specific category.

The PTs will be listed for summary within each category in decreasing risk difference.

The additional data collected on the ISR follow-up forms will be summarized in 2 distinct ways:

1. at the participant-level (each participant contributes to totals at most once, regardless of the number of ISR events the participant experienced), and
2. at the event level (each separate event contributes to totals, regardless of whether the participant experienced multiple ISR events).

4.6.2.1.5. *Neoplasms*

The TEAEs of neoplasms will be identified by narrow search for the following SMQ:

- Malignant tumours SMQ (20000194, narrow terms), and
- Tumours of unspecified malignancy SMQ (20000195, narrow terms).

A summary will present:

- Any narrow term from any 1 of the 2 SMQs indicated above (that is, combined search across narrow portions of both SMQs), and
- Any narrow term within each SMQ, separately (that is, narrow SMQ search).

4.6.2.1.6. *Diabetic Ketoacidosis (DKA)*

DKA will be searched by MedDRA PTs from all TEAEs. The number and percentage of participants experiencing treatment-emergent DKA will be summarized. The TEAEs of DKA will be identified using MedDRA PTs of:

- Diabetic ketoacidosis,

- Ketoacidosis,
- Euglycaemic diabetic ketoacidosis,
- Ketonuria,
- Diabetic ketosis,
- Diabetic ketoacidotic hyperglycaemic coma,
- Ketosis,
- Urine ketone body present,
- Blood ketone body,
- Blood ketone body increased,
- Urine ketone body,
- Blood ketone body present, and
- Lactic acidosis.

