4.6.2.1.8. Peripheral Edema

The peripheral edema will be searched by MedDRA PTs (see Section 6.8) from all TEAEs. The number and percentage of participants experiencing treatment-emergent peripheral edema will be summarized by PT.

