6.8. Appendix 8: MedDRA PT for Peripheral Edema

The analysis of peripheral edema (Section 4.6.2.1.8) will be based on the TEAEs in the following terms:

- Acute pulmonary oedema
- Ascites
- Brain oedema
- Bronchial oedema
- Capillary leak syndrome
- Cerebral oedema management
- Compression garment application
- Cytotoxic oedema
- Effusion
- Fluid retention
- Gastrointestinal oedema
- Generalised oedema
- Gravitational oedema
- Hydraemia
- Hypervolaemia
- Hypoosmolar state
- Lipoedema
- Lymphoedema
- Negative pressure pulmonary oedema
- Non-cardiogenic pulmonary oedema
- Non-pitting oedema
- Oedema
- Oedema blister
- Oedema due to cardiac disease
- Oedema due to hepatic disease
- Oedema due to renal disease
- Oedema mucosal
- Oedema peripheral
- Pelvic fluid collection
- Pericardial effusion
- Perinephric collection
- Perinephric oedema
- Peripheral swelling
- Pleural effusion
- Pulmonary oedema
- Retroperitoneal effusion
- Retroperitoneal oedema
- Skin oedema
- Skin swelling
- Subdural effusion
- Swelling
- Visceral oedema

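### The count labelled treatment-emergent DKA pools 13 terms of which only 4 name ketoacidosis, so it can be overstated; the peripheral edema label has a lesser version of the same mismatch.

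*SAP*

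**What the plan says.** SAP 4.6.2.1.6 (Diabetic Ketoacidosis) reports one measure: "The number and percentage of participants experiencing treatment-emergent DKA will be summarized". The case definition follows: "The TEAEs of DKA will be identified using MedDRA PTs of" a list of 13 PTs. That list includes "Blood ketone body increased" and "Lactic acidosis".

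SAP 4.6.2.1.8 (Peripheral Edema) says: "The number and percentage of participants experiencing treatment-emergent peripheral edema will be summarized by PT". SAP Appendix 8 supplies the terms, introduced by "The analysis of peripheral edema (Section 4.6.2.1.8) will be based on the TEAEs in the following terms". The list has 42 PTs, one of which is "Pericardial effusion".

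Three other provisions bear on the point:

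- The adverse event table in SAP 4.6.2 plans a display for all safety topics of interest: "TEAE of safety topic of interest by PT (within SMQ when applicable". DKA and edema are both such topics.
- SAP 4.6 applies Fisher's exact test, with a risk difference and 95% confidence interval, unless something else is noted. Nothing else is noted for DKA.
- Protocol 10.3.1 makes a laboratory result an adverse event only when the investigator judges it clinically significant.

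**The concern.** A reader of the study report will take a row headed DKA to mean participants who had ketoacidosis. Under the stated rule it means participants with any of 13 reported terms, most of which describe something else. Lactic acidosis is a different condition, and a ketone finding in blood or urine is not by itself ketoacidosis.

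Ketoacidosis is a serious event, and its count in each arm is a figure that readers will look for. If the true number is small, a few participants with only a ketone term could change the percentage and the between-arm comparison. The label on the edema search raises a milder form of the same question, because its list reaches well beyond the limbs.

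**Working it through.** The plan gives no DKA or edema rate, so there is no figure of its own to reproduce. The check has three parts: counting the terms, seeing what pooling can do to the count, and seeing what the display by PT can recover.

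**1. DKA list (SAP 4.6.2.1.6)**

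| Group | PTs | Number |
|---|---|---|
| Names ketoacidosis | Diabetic ketoacidosis; Ketoacidosis; Euglycaemic diabetic ketoacidosis; Diabetic ketoacidotic hyperglycaemic coma | 4 |
| Ketosis | Ketosis; Diabetic ketosis | 2 |
| Ketonuria | Ketonuria | 1 |
| Ketone laboratory terms | three for blood, two for urine | 5 |
| Other | Lactic acidosis | 1 |

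Total: 4 + 2 + 1 + 5 + 1 = 13. Not ketoacidosis: 9 of 13, or 69%.

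**2. Effect of pooling**

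Let c be the participants in an arm with at least one of the four ketoacidosis PTs. Let k be those with only one or more of the other nine. The reported count is c + k, so within an arm it can be too high but never too low. It is exact when k = 0.

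SAP section 5 plans 888 randomized 1:1, so 888 / 2 = 444 per arm. This is an approximate denominator, because the safety set requires at least one dose. The reported percentage is 100 × (c + k) / 444. The event counts below are assumed, for illustration only:

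| c | k = 0 | k = 1 | k = 3 | k = 5 |
|---|---|---|---|---|
| 0 | 0.00% | 0.23% | 0.68% | 1.13% |
| 1 | 0.23% | 0.45% | 0.90% | 1.35% |
| 2 | 0.45% | 0.68% | 1.13% | 1.58% |

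The between-arm difference can move either way. Suppose one arm has c = 2, k = 0 and the other has c = 0, k = 2. The reported counts are 2 and 2, a difference of 0, while the ketoacidosis difference is 2 / 444 = 0.45 percentage points. Conversely, with c = 0 in both arms and k = 3 in one arm only, the table shows a difference of 0.68 points where no ketoacidosis occurred.

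**3. What the rows by PT recover**

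Each PT row counts participants with that term. The number with any ketoacidosis PT lies between the largest of the four rows and their sum, because one participant may have two of the terms. Two rows showing 1 each could be one participant or two. The display therefore shows which terms were reported, but it does not give the de-duplicated narrow count or a risk difference for it.

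**4. Edema list (SAP Appendix 8)**

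Of 42 PTs, 2 contain the word peripheral. About 20 name an internal organ, a cavity or an effusion:

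- 4 pulmonary edema terms
- 3 brain-related terms
- 5 effusion terms
- 2 perinephric terms
- 6 single terms: ascites, bronchial, gastrointestinal, pelvic, retroperitoneal and visceral

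The sum is 4 + 3 + 5 + 2 + 6 = 20, or 20 / 42 = 48%. The remaining 42 − 2 − 20 = 20 are generalized, skin, unspecified or fluid-status terms, with a few others such as a compression garment term.

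**5. Comparison with the SAP's other searches**

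Hypersensitivity (4.6.2.1.3) uses narrow query terms and case review of notable events. Neoplasms (4.6.2.1.5) use narrow terms. Medication errors (4.6.2.1.12) state that both narrow and broad terms are used, then restrict by deviation criteria. Hepatic disorders (4.6.3.2) use mostly broad terms under a heading that says the events are only potentially drug-related. The DKA section combines a broad list with a specific diagnosis, and has no narrow count, case review or statement of breadth.

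**The case against.** The case on the other side is substantial:

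- **Separation by term is largely planned.** The table in SAP 4.6.2 covers every safety topic by PT, and 4.6.2.1.8 says so directly for edema. Serious events also appear by PT within system organ class and in individual listings. A reader might infer that a serious effusion would be hidden under peripheral edema. The documents do not support that, because a pleural effusion would appear under its own name.
- **Laboratory findings are filtered.** Ketones are part of the urinalysis (Protocol 10.2), but a result becomes an adverse event only through the clinical-significance judgement in Protocol 10.3.1. That judgement is made in an open-label trial, so it reduces the problem without removing it.
- **Wide safety searches are legitimate and occur elsewhere.** The retinopathy list in Appendix 7 includes Diplopia and Vision blurred. Sensitivity is a reasonable aim in screening for safety signals.
- **The consequence is limited.** Neither topic is an endpoint in SAP 1.1, and SAP 2.1 makes no multiplicity-controlled claim on safety.
- **A program-level plan exists.** The version history ties several safety revisions to the PSAP, which is not available here. Whether these lists are harmonized across studies cannot be checked.

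All of this stands, and it settles the severity as minor. It does not answer two points: the rows by PT do not yield the participant count for ketoacidosis, and the default test and risk difference would attach to the mixed count.

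**Conclusion.** The DKA label does not match its definition. The pooled count can overstate DKA, and its between-arm difference can be distorted in either direction, if any participant has a listed term but none of the four ketoacidosis PTs. Each such participant adds about 0.23 percentage points in an arm of 444. The documents give no event counts, so the actual size is unknown and may be zero.

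Two stronger readings are tempting. A reader might infer that both reported counts will be wrong. That does not follow, since the DKA count is exact when no such participant exists and the edema results are set out by PT. A reader might also infer that most edema terms are not peripheral. The list shows about 20 of 42 naming an internal site, cavity or effusion. Many of the others, such as unspecified edema or swelling, could describe the limbs.

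The edema half is therefore a labelling matter only. Severity is minor overall. The primary and key secondary analyses and their error control are untouched.

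**What to change.** **DKA (SAP 4.6.2.1.6)**

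1. Keep the 13-term search and rename it, for example 'ketosis/acidosis-related terms'.
2. Prespecify beside it the number and percentage of participants with at least one of the four ketoacidosis PTs, with the risk difference and 95% confidence interval.
3. Show lactic acidosis as its own row.

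**Edema (SAP 4.6.2.1.8 and Appendix 8)**

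Rename the search, for example 'edema, effusion and fluid-related terms', and keep the planned display by PT. Do not restrict the count to the two PTs that contain the word peripheral, because that could miss limb edema coded to an unspecified term.

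**Cost**

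The change adds about one row per table and needs a safety physician to check the narrow list. It may also need alignment with the program-level plan. No new data are needed and the broad search loses no sensitivity. SAP 4.1 allows a change of this kind to be recorded in the SAP or the clinical study report without a protocol amendment. It is best made before unblinding.
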